Reason for ALK inhibitor (alectinib, and subsequent treatment) treatment discontinuation	Chart review	Treatment characteristics	Study observation period	Data for alectinib and subsequent treatment discontinuation reason will exclusively come from chart review. Reviewers will be asked to select reason(s) as explicitly documented in patients' charts. If available, reason patients discontinued treatment will be abstracted: Completion of therapy Provider-documented disease progression Death Insurance/cost-related Loss to follow-up Patient preference Toxicity Other No information Reviewers will specify other reasons; these will be reported if any represent >5% of patients.	
ALK inhibitor treatment sequencing	iKM structured data + chart review	Treatment pattern	Study observation period	ALK inhibitor treatment paths (e.g. initiate crizotinib followed by ceritinib, initiate crizotinib followed by alectinib, etc.)	
Front-line alectinib	iKM structured data + chart review	Treatment pattern	Study observation period	First treatment administration of alectinib not preceded by any other product for NSCLC therapy except up to 3 months of chemotherapy and immunotherapy preceding alectinib therapy initiation to classify patient as receiving 1L alectinib	
Clinical outcomes					
Last US Oncology Network visit date	iKM structured data + chart review	Clinical outcomes	Study observation period	Each patient's most recent visit date, prior to or on close of study observation period, in the structured data will be recorded. A visit is defined as a physician encounter with the practice where either treatment is given, or vital signs are recorded. For patients with a death date, this last visit date should occur prior to the death date.	

Table 1. Study variables and operational definitions

Variable	Source(s)	Role(s) in study	Period of measurement	Operational definition
				This will not be reported separately; it will be used in calculating the patient's available follow-up time as a descriptive measure. Available follow-up time = Integer (latest of last visit date or death date – index date +1).7

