9.6. Study size

A preliminary feasibility assessment for Phases 1 and 2 identified 293 patients who were treated with alectinib after 01 November 2017, with approximately half treated in the front-line setting. Of the 293 patients receiving alectinib, 74% (n=217) patients had an ALK result. Approximately 20-30% of the 293 patients received a subsequent therapy after alectinib. It is estimated that approximately 300 patients will be included in the Phase 2 structured data analysis. Targeted chart review for Phase 2 is proposed to occur on 150 patients receiving alectinib to identify at least 100 patients who received alectinib as front-line. In the event the total number of eligible patients following structured data screening exceeds the planned number of charts for review, a random sample will be selected.

For Phase 3 structured analysis, a preliminary feasibility assessment identified 521 patients who were treated with alectinib from 01 June 1 2017 through 31 December 2020. Chart review for Phase 3 will include patients who had ongoing treatment at the end of Phase 2

study period, and an additional 125 patients will be targeted to identify 100 new patient who received alectinib as front-line therapy. For Phase 3 exploratory analysis, a preliminary feasibility assessment identified 134 patients who were treated with lorlatinib from 01 November 2018 through 31 December 31 2020.

The final study population for analysis will be defined after identification and review of the patient population meeting the eligibility criteria in the iKM database. A specific power calculation will not be performed as this is a descriptive analysis.

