9.8.3. Statistical methods

Description of study enrollment

To be included in the study patients must meet each of the inclusion criteria and none of the exclusion criteria listed in Section 9.3.1. Counts of patients excluded for each criterion will be summarized.

Additionally, the counts of patients to be classified into the following subgroups will be presented⁵:

- Cohort A: All alectinib treated patients (overall population)
- Cohort B (Alectinib only cohort): Alectinib treatment ongoing, or discontinued and no subsequent treatment⁶
- Cohort C: Alectinib followed by treatment X (top 3 most frequent)
- Cohort D: Alectinib followed by treatment Y (top 3 most frequent)
- Cohort E: Alectinib followed by treatment Z (top 3 most frequent)

Description of patient demographic, clinical and treatment characteristics

Descriptive analyses will be conducted to evaluate the demographic, clinical and treatment characteristics overall, as well as for each of the study cohorts. Results will be reported in

⁵ Final cohorts will be decided upon sample size. Patients receiving chemotherapy after initiating alectinib will be included in the patient sample

⁶ Patients with ongoing alectibin treatment, patients who discontinued alectinib and patients who did not have a subsequent treatment may be analyzed as separate cohorts depending on sample size of patients

aggregate. Categorical variables (e.g., ECOG performance status) will be reported as frequency and percentage. Continuous variables such as age will be reported as mean, standard deviation, median and range (minimum-maximum). In the case of missing observations, the number and percentage of missing values will be reported.

For comparative analysis, i.e. comparing 2 or more treatment groups (e.g., ALK inhibitor sequences) or strata (front-line alectinib and non front-line alectinib), statistical significance will be reported with level of statistical significance based on p = 0.05 level as well as 95% confidence intervals.

Chi-square testing will be used to assess associations between categorical variables when patient counts for single cells within the results tables are greater or equal to 5. When distribution cannot be assumed to be Chi-square, then Fisher's exact test will be used. Depending on normality, Analysis of variance (ANOVA)/t-tests or Kruskall-Wallis tests will be used for continuous variables. An alpha level of 0.05 will be the primary criterion for statistical significance of this study.

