All descriptive tables will be presented for each of the study cohorts defined above and, as supported by the final sample size, stratified by front-line alectinib and non front-line alectinib treatment groups.

For Phase 3 exploratory objectives, descriptive analyses will be conducted to evaluate the demographic, clinical and treatment characteristics among patients treated with lorlatinib. Results will be reported in aggregate. Categorical variables (e.g., ECOG performance status) will be reported as frequency and percentage. Continuous variables such as age will be reported as mean, standard deviation, median and range (minimum-maximum). In the case of missing observations, the number and percentage of missing values will be reported.

Clinical outcomes

ALK inhibitor DOT, OS, PFS will be assessed using the Kaplan-Meier method with 95% CIs, and summary tables of the number of events and censored patients at 3, 6, 12, 18, and 24 months. Further details about these calculations are presented below and in Table 1.

Clinical outcome results will be presented by study cohort and stratified by front-line alectinib and non-front line alectinib (pending sample size).

Overall survival (OS) will be defined as the interval between start date of alectinib to the date of death as documented in the LADMF and/or iKM EHR database. Patients who did not die will be censored on the study end date or the last visit date available in the database, whichever occurred first. In order to handle censoring, the Kaplan-Meier method will be used to calculate median overall survival with 95% confidence intervals (in number of months). Additionally, 3, 6, 12, 18, and 24-month survival probabilities will be reported. OS will be estimated for the full study population and stratified by study cohort. Log-rank tests will be used to assess statistical differences.

Duration of Therapy (DOT) for ALK inhibitors: An intent to treat approach will be used. DOT will be defined as duration of time (in months) between alectinib treatment initiation and discontinuation, or the last administration date of alectinib, or start date of a subsequent ALK inhibitor, initiation of any subsequent non-ALK inhibitor treatment (as a proxy for evidence of discontinuation), death or check-in in a hospice will be used as a stop date.

There may be some patients who do not have evidence of discontinuation or who do not move on to a subsequent therapy.

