Descriptive statistics (mean, median) and K-M methodology will be calculated from initiation of alectinib, until evidence of discontinuation for any reason, including but not limited to a treatment stop date, a last alectinib administration date, or evidence of new ALK inhibitor treatment or non-ALK inhibitor treatment. Patients who do not have evidence of discontinuing, starting new therapy, or whose last prescription date is <30 days from the end of the study period, will be censored at last visit date or end of study period.

$$DOT = (\frac{\textit{date of ALK treatment discontinuation - index date} + 1}{30.4375})$$

Progression-free survival: The PFS will be measured from the initiation of alectinib to the date of progression or date of death due to any cause, censoring patients who are still alive at the end of the study observation period and did not progress at the last visit date. Progression will be clinician-noted progression as noted per physician notes only, not by traditional Response Evaluation Criteria in Solid Tumors (RECIST) imaging, as this is impacted by frequency of imaging and may not be assessed the same across groups in daily clinical practice. Patients who did not progress or die will be censored on the study end date or the last visit date available in the database, whichever occurred first. The PFS will be estimated in months using the Kaplan-Meier method with 95% CIs, and summary tables of the number of events and censored patients at 3, 6, 12, 18, and 24 months. PFS will be estimated for the full study population and separately by study cohort. Log-rank tests will be used to explore statistical differences.

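### The descriptive mean and median of duration of therapy, planned beside Kaplan-Meier, are not valid estimates in groups where patients are still on treatment at the data cut

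*Combined protocol and SAP*

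**What the plan says.** The clinical outcomes part of section 9.8.3 opens with "ALK inhibitor DOT, OS, PFS will be assessed using the Kaplan-Meier method with 95% CIs" and adds counts of events and censored patients at five time points. The DOT text in the same section then adds a second kind of summary: "Descriptive statistics (mean, median) and K-M methodology will be calculated from initiation of alectinib, until evidence of discontinuation for any reason". Table 1 (section 9.4) repeats that sentence.

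The plan expects censoring. It notes that "There may be some patients who do not have evidence of discontinuation or who do not move on to a subsequent therapy", and patients without evidence of stopping "will be censored at last visit date or end of study period". It does not say how they enter the mean and median. The DOT formula in section 9.8.3 uses only a discontinuation date. The Table 1 entry on treatment end dates covers stop dates missing because the patient died, was lost or is still on treatment. It substitutes the earliest of the last treatment, death and study-end dates.

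For overall survival (OS), section 9.8.3 takes the median from Kaplan-Meier and gives censoring as the reason. It names the log-rank test for OS and progression-free survival (PFS) but not for DOT. Table 1 classes DOT as a treatment characteristic, and section 9.8.3 assigns ANOVA, t-tests or Kruskal-Wallis to continuous variables. Section 9.8 says that no separate analysis plan will be written.

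**The concern.** A simple mean or median can handle a patient still on treatment in only two ways: count the time so far as a finished duration, or leave the patient out. Neither estimates DOT. The first shortens the long durations. The second keeps mainly those who stopped early. Both depend on how long patients have been observed, so a later cut gives a larger figure even when prescribing is unchanged.

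DOT is the quantity named in Objectives 3 and 7, and the study reports it at two cuts. The report could carry two conflicting medians for one outcome, and the rise at the Phase 3 refresh could be read as better persistence. If DOT is handled as an ordinary continuous variable, group comparisons would also ignore censoring.

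**Working it through.** The plan states no DOT figure or number still on treatment, so there is nothing of its own to reproduce.

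**Inputs from section 9.3.** Phases 1 and 2 identify patients from 1 June 2017 to 30 June 2019 (25 months) and cut at 31 December 2019, so potential follow-up runs from a = 6 to b = 31 months. Phase 3 identifies patients to 31 August 2020 (39 months) and cuts at 31 August 2021, so a = 12 and b = 51.

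**Assumptions.** Entry is uniform, nobody is lost, and DOT is exponential with rate λ = ln 2 / median. Two true medians are used: 25.7 months (the first-line PFS median cited in section 7, as a stand-in only) and 12 months. The true means are 25.7/0.6931 = 37.1 and 12/0.6931 = 17.3 months.

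**Formulas**, with censored time counted as duration:
- Share still on treatment: p = (e^(−λa) − e^(−λb)) / (λ(b − a))
- All-patient mean: (1 − p)/λ
- All-patient median: the t that solves e^(−λt) × S(t) = 0.5, where S(t) = 1 for t ≤ a and (b − t)/(b − a) after that

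**True median 25.7 (λ = 0.02697)**
- First cut: p = (0.8506 − 0.4334)/0.6743 = 0.62. Mean = 37.1 × 0.381 = 14.1. At t = 13.2: 0.70 × 0.71 = 0.50.
- Second cut: p = (0.7235 − 0.2527)/1.0519 = 0.45. Mean = 37.1 × 0.552 = 20.5. At t = 18.7: 0.604 × 0.828 = 0.50.

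**True median 12 (λ = 0.05776)**
- First cut: p = (0.7071 − 0.1669)/1.4441 = 0.37. Mean = 17.3 × 0.626 = 10.8. At t = 9.4: 0.581 × 0.864 = 0.50.
- Second cut: p = (0.5000 − 0.0526)/2.2527 = 0.20. Mean = 17.3 × 0.801 = 13.9. At t = 12: 0.50 × 1 = 0.50, so the median is correct. Nobody can be censored before 12 months.

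The last two columns below come from simulation under the same assumptions. All times are in months.

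| True median | Cut | Still on treatment | Mean, all | Median, all | Median, discontinuers only | Kaplan-Meier median |
|---|---|---|---|---|---|---|
| 25.7 | Dec 2019 | 62% | 14.1 | 13.2 | about 8 | 25.7 |
| 25.7 | Aug 2021 | 45% | 20.5 | 18.7 | 12.0 | 25.7 |
| 12 | Dec 2019 | 37% | 10.8 | 9.4 | 6.5 | 12.0 |
| 12 | Aug 2021 | 20% | 13.9 | 12.0 | 8.9 | 12.0 |

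**Drift in a fixed group.** If the Phase 1/2 patients alone are followed to 31 August 2021 (true median 25.7), the mean goes from about 14 to 23.7 with no change in true DOT.

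**Sensitivity.** The simulation was repeated with Weibull shapes 0.8, 1.0 and 1.3 and true medians of 10.4, 12, 18, 25.7 and 30 months. Between 28% and 70% were still on treatment at the first cut and 11% to 50% at the second. The simple mean was below the true mean in every scenario. The simple median was also low, except the all-patient median at the second cut when the true median was 12 months or less. The Kaplan-Meier median stayed within 0.2 months of the truth. With 1% loss per month (exponential, true median 25.7), the all-patient mean falls to 12.9 then 17.9.

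**The case against.** The strongest reply is that the valid analysis is already there. Kaplan-Meier with confidence intervals is the named method for DOT, a censoring rule follows, and the study is descriptive. That stands: the fault lies in an added summary. A reader might infer that DOT has no sound analysis, and the documents do not support that.

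The text could also mean a Kaplan-Meier median and a restricted mean. It does not exclude this. But it lists descriptive statistics apart from Kaplan-Meier, substitutes dates for missing stop dates and leaves no later plan to settle the matter, so the simple reading is the natural one.

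Three stronger readings go beyond the documents:
- **That most patients are known to be still on alectinib.** Section 9.6 says "Approximately 20-30% of the 293 patients received a subsequent therapy after alectinib", which leaves about 205 to 234 of 293 without one. That group mixes ongoing patients with those who died or stopped without further treatment. Cohort B is defined the same way: "Cohort B (Alectinib only cohort): Alectinib treatment ongoing, or discontinued and no subsequent treatment". No count of ongoing patients is given.
- **That every simple DOT figure is biased.** Alectinib DOT in cohorts C to E is uncensored, because each patient has moved to a next treatment. Simple summaries there validly describe patients selected for having moved on.
- **That available follow-up time in Table 1 has the same flaw.** It is the time actually observed for each patient, "used in calculating the patient's available follow-up time as a descriptive measure", and is not a censored treatment duration.

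The 25.7-month example is also generous. It is a PFS median from a first-line trial, while section 9.6 describes its feasibility patients as "approximately half treated in the front-line setting". The 12-month case shows a smaller effect.

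**Conclusion.** The point holds for groups with patients still on treatment at the cut: alectinib DOT in cohorts A and B, and DOT of post-alectinib treatment. There, a simple mean is too low, a simple median usually is, and both generally rise from the first cut to the second with no change in persistence. The direction follows from the censoring. The size rests on the assumed DOT distribution, uniform entry and an unknown share still on treatment. It ranges from a halving of the median at the first cut (13.2 against 25.7) to no error in the all-patient median at the second cut when the true median is 12 months. The plan should be corrected before the Phase 3 analysis, but its main DOT analysis is not undermined.

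**What to change.** In section 9.8.3 and the DOT row of Table 1:
- For any group with censored patients, replace the descriptive mean and median with the Kaplan-Meier median and quartiles with 95% CIs.
- If a mean is wanted, give a restricted mean to a stated horizon that the follow-up supports. At the first cut, 24 months of potential follow-up exists only for entrants up to 31 December 2017, about 7/25 = 28% of a uniform intake.
- Label any observed-time mean or median that is kept as time on treatment to data cut, with the number ongoing beside it.
- State that DOT comparisons use the log-rank test, as for OS and PFS, and not ANOVA, t-tests or Kruskal-Wallis. This handles the censoring. It does not remove the selection of cohorts C to E on a later event.

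Simple summaries of alectinib DOT in cohorts C to E can stay. The cost is a few sentences and a few lines of code, with no new data. Some medians may be reported as not reached, and restricted means may be imprecise in small cohorts.

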8. RESEARCH QUESTION AND OBJECTIVES

The overall goal of this study is to understand the patient characteristics, treatment patterns, and clinical outcomes of ALK+ NSCLC patients treated with alectinib in US community oncology practices. To efficiently and effectively address research questions, we will leverage both the structured and unstructured data of the EHR and execute the study in 2 phases. Phase 1 will consider a population of ALK+ NSCLC patients who received alectinib during the study intake period. For Phase 2, a sample of patients who received alectinib as front-line therapy will be selected for chart review.

The study plan utilizes structured data and unstructured (chart review data). For the landscape objectives in Phase 1, study data will originate from structured fields of the EHR, which are controlled and mapped data elements, and will be available ahead of chart review data. For the second phase, specific study objectives will be assessed among a subset of patients selected for chart review using both structured and unstructured data. In this phase, data will also be derived from unstructured fields in the EHR, such as providers' free-text notes, which can only be captured through a chart review.

Phase 1: Landscape Objectives (structured data):

These analyses will be performed for all study-eligible patients who received alectinib (in any line of therapy) during the study identification period. Results will be presented overall as well as for the subgroups of patients who received a subsequent therapy following alectinib:

- 1. Describe the demographic and clinical characteristics of ALK+ NSCLC patients who received alectinib overall, and stratified by subsequent treatment following alectinib
- 2. Characterize post-alectinib treatment patterns and sequencing of other ALK inhibitors; categorizing type of treatments received after alectinib
- 3. Estimate duration of therapy with alectinib and duration of therapy for post-alectinib treatment
- 4. Examine overall survival of patients post-alectinib stratified by subsequent treatment following alectinib

Phase 2: Chart Review Objectives (unstructured data):

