Overall survival (OS) (alectinib and stratified by subsequent treatment)	iKM structured data + LADMF + chart review (derived)	Clinical outcomes	Study observation period	OS will be defined as the interval (in months) between alectinib start date and the date of death (any cause) as documented in the LADMF and the iKM EHR database. OS will be reported for overall alectinib and stratified by subsequent treatment. Patients who did not die within the study observation period will be censored on the study end date or the last visit date available in the dataset, whichever occurred first. OS will be analyzed using the Kaplan-Meier method with 95% CIs, and summary tables of the number of events and censored patients 3, 6, 12, 18, and 24 months.
Progression date after index date (physician- assessed)	Chart review	Clinical outcomes	Study observation period	Physician-assessed disease progression (and corresponding date of note) recorded from physician's progress notes in Chart Review.
Progression- free survival (alectinib, and subsequent treatment)	iKM structured data + LADMF + chart review (derived)	Clinical outcomes	Study observation period	The PFS will be measured from the initiation of alectinib to the date of progression or date of death due to any cause, censoring patients who are still alive at the end of the study observation period and did not progress at the last visit date. PFS will be reported for overall alectinib and stratified by subsequent treatment. The PFS will be estimated in weeks using the Kaplan-Meier method with 95% CIs, and summary tables of the number of events and censored patients at 3, 6, 12, 18, and 24 months.

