9.8.1. Analysis sets

Phases 1 and 2

For analyses performed to meet the Phase 1 objectives, all patients who the meet the eligibility criteria defined in Section 9.3.1 will be considered. The study cohorts will be identified based on subsequent therapy following alectinib. For these analyses, datasets consisting of the structured data elements, plus the LADMF to confirm vitality status, required for the landscape analyses will be constructed.

The Phase 2 (chart review) analyses will be limited to a sample of 100 qualified front-line alectinib patient charts identified from Phase 1. The chart review analysis sets will be constructed from both structured and unstructured data, with the LADMF used to confirm vitality status.

Phase 3

For analyses performed to meet the Phase 3 unstructured objectives, all patients who the meet the eligibility criteria defined in Section 9.3.1 will be considered. The study cohorts will be identified based on subsequent therapy following alectinib. For these analyses, datasets consisting of the structured data elements, plus the LADMF to confirm vitality status, required for the landscape analyses will be constructed.

Phase 3 chart review analyses will include a subset of patients from Phase 2 chart review who had ongoing treatment at the end of the observation period and an additional sample of 100 qualified front-line alectinib patients from Phase 3. The chart review analysis sets will be constructed from both structured and unstructured data, with the LADMF used to confirm vitality status.

Some data elements will be captured with both structured and unstructured data. Since the chart review data are expected to provide a richer source of information, if data are available from both sources for a single patient, then chart review data will supersede what is available in the structured iKM data for the final analysis. To account for this, a final analysis data set will be constructed and used to update the landscape analyses once chart review data are available.

For Phase 3 exploratory analysis, all patients who meet the eligibility criteria defined in Section 9.3.2 will be considered. The study cohorts will be identified based on subsequent therapy following lorlatinib. For these analyses, datasets consisting of the structured data elements will be constructed.

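### Section 9.8.3 asks for PFS in the full study population and by line of alectinib, but progression is collected only in chart-reviewed front-line patients, the set to which Objective 9 and Section 9.8.1 confine it

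*Combined protocol and SAP*

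**What the plan says.** **The broad instruction.** The PFS paragraph of Section 9.8.3 states "PFS will be estimated for the full study population and separately by study cohort", followed by log-rank tests. The Clinical outcomes text of the same section, which covers duration of therapy, OS and PFS together, adds: "Clinical outcome results will be presented by study cohort and stratified by front-line alectinib and non-front line alectinib (pending sample size". The Data analysis part of the abstract (Section 4) applies the same split to all analyses, as the final sample size supports. Section 9.8.3 defines the overall population in its cohort list: "Cohort A: All alectinib treated patients (overall population".

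**Where progression comes from.** Table 1 (Section 9.4) names chart review as the only source of the progression date: "Physician-assessed disease progression (and corresponding date of note) recorded from physician's progress notes in Chart Review". Section 9.8.3 agrees: "Progression will be clinician-noted progression as noted per physician notes only". Section 8 describes unstructured fields "such as providers' free-text notes, which can only be captured through a chart review". Deaths, by contrast, come from the death master file and the EHR for every patient (Table 1).

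**The narrower instruction.** PFS is Objective 9, listed only under the Phase 2 chart review (Sections 4 and 8). Section 9.8.1 says: "The Phase 2 (chart review) analyses will be limited to a sample of 100 qualified front-line alectinib patient charts identified from Phase 1". Phase 3 adds about 100 further front-line charts and extends follow-up for Phase 2 chart patients who were still on treatment.

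**The concern.** Section 9.8.3 gives PFS a wider population than the one in which progression is observed. Its censoring rule ends follow-up at study end or last visit for anyone who neither progressed nor died. It does not separate a patient whose reviewed chart shows no progression from a patient whose chart was never opened. Section 9.5 merges all sources into one master dataset, so a program written from Section 9.8.3 would run without error and treat every unreviewed patient as progression-free until death or censoring.

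Three results would be affected:

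- Overall PFS would be too high.
- The non-front-line PFS curve would equal the OS curve, so a comparison by line would set progression or death against death alone.
- Comparisons between subsequent-treatment cohorts would partly reflect who had a chart reviewed, because the added Phase 3 charts are chosen from named subsequent-treatment groups (Section 9.3.4.2).

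**Working it through.** The plan makes no power or event calculation, so there is no design figure to reproduce. Its one checkable feasibility figure is right: 217/293 = 74.1%, stated as 74% (Section 9.6).

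**Step 1. Patients with no source of progression.** Inputs: about 300 structured-data patients in Phases 1 and 2, and a Phase 3 feasibility count of 521 (Sections 4 and 9.6); 100 qualified charts in Phase 2 and 100 more in Phase 3 (Section 9.8.1).

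- Phases 1 and 2: 300 − 100 = 200, and 200/300 = 67%.
- Phase 3: 521 − (100 + 100) = 321, and 321/521 = 62%.
- If every chart opened supplied progression (150 + 125 = 275): 521 − 275 = 246, and 246/521 = 47%.

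The 521 is a feasibility count to 31 December 2020, whereas the Phase 3 identification period ends on 31 August 2020, so the final denominator will differ. About half of the 293 Phase 1 and 2 feasibility patients were non-front-line (roughly 147). None of these belongs to the qualified chart sample.

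**Step 2. Illustration of the bias at 24 months, a planned reporting time.** Let w be the share of patients with abstracted progression. Read literally, the estimate tends to

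S(24) = w × 0.5^(24/mPFS) + (1 − w) × 0.5^(24/mOS).

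Assumptions:

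- Both curves are exponential.
- mPFS = 25.7 months, from the first-line trial cited in Section 7.
- mOS = 81.6 months (6.8 years × 12, Section 7, counted from diagnosis and not from alectinib start), with 40 months as an assumed lower value.

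Components: 0.5^(24/25.7) = 0.523; 0.5^(24/81.6) = 0.816; 0.5^(24/40) = 0.660.

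| w | mOS (months) | Calculation | Apparent 24-month PFS | With progression known for all |
|---|---|---|---|---|
| 100/300 = 0.333 | 81.6 | 0.333 × 0.523 + 0.667 × 0.816 | 72% | 52% |
| 200/521 = 0.384 | 81.6 | 0.384 × 0.523 + 0.616 × 0.816 | 70% | 52% |
| 100/300 = 0.333 | 40 | 0.333 × 0.523 + 0.667 × 0.660 | 61% | 52% |
| 200/521 = 0.384 | 40 | 0.384 × 0.523 + 0.616 × 0.660 | 61% | 52% |

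With all 275 charts usable (w = 0.528) the apparent figure is 59% (mOS 40) to 66% (mOS 81.6).

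**Step 3. Sensitivity to the PFS input.** About half the structured-data population is not front-line, so 25.7 months may be too long. With an assumed mPFS of 15 months and mOS of 48 to 81.6 months, apparent 24-month PFS is 56 to 65% against 33%. The gap widens.

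No apparent median is given. Maximum follow-up is 51 months (01 June 2017 to 31 August 2021), few patients can be observed that long, and a late median might not be estimable.

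**The case against.** The strongest reply is that the PFS population is already fixed elsewhere. PFS appears only as Objective 9, under the chart review. The Phase 1 objectives do not include it, and Section 9.8.1 limits Phase 2 analyses to the chart sample. On that reading the full study population means the whole chart sample as opposed to its cohorts. The split by line is conditional on sample size and would lapse if no non-front-line charts exist. Section 9.8.2 requires missing data to be reported, with a decision to include, exclude or impute a variable when much is missing.

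Much of this stands. A reader might infer that the study intends PFS for all treated patients and will report a seriously inflated figure. The documents do not support that, because Objective 9 and Section 9.8.1 point the other way. Nor is a log-rank test of PFS by line stated outright. It has to be pieced together from the general text on comparisons in Section 9.8.3 and the sentence on stratification. The sentence next to the PFS log-rank test concerns cohorts.

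It does not dispose of the point:

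- Section 9.8.3 uses the same phrase for OS, where it does cover every structured-data patient.
- In Section 9.8.1 the Phase 3 paragraph assigns the unstructured objectives to all eligible patients while describing a structured dataset. This is probably a slip, but it leaves the Phase 3 PFS set less clear than the Phase 2 one.
- The sample-size condition counts patients, not abstracted progressions, so a large non-front-line stratum could pass it with no progression data.
- The missing-data provision is general, and an unopened chart need not appear as missing under the censoring rule.
- Section 9.8 says no separate analysis plan will be written, so no later document is planned to settle the matter.

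**Conclusion.** The concern holds as a conflict within the protocol. Section 9.8.3 sets a wider PFS population than Objective 9, Section 9.8.1 and the progression source in Table 1 allow. On any reading, PFS in non-front-line patients cannot be estimated from the planned data.

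If Section 9.8.3 is followed literally, about two thirds of patients in Phases 1 and 2, and about 62% of the Phase 3 feasibility count, can contribute only deaths, and PFS is biased upward. The direction follows from the censoring rule. The size (24-month PFS of about 61 to 72% instead of 52%) is an illustration. It rests on exponential curves, a first-line trial median applied to a mixed-line population, and an OS median that is either counted from diagnosis or assumed. It should not be read as a forecast of the study's result.

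**What to change.** In Section 9.8.3, state that PFS is estimated, overall and by cohort, only among chart-reviewed front-line patients, and exempt PFS from the front-line versus non-front-line stratification and from any log-rank test on it. Make the PFS entry in Table 1 (which reports PFS for alectinib overall) and the Data analysis paragraph of the abstract match. The Phase 3 paragraph of Section 9.8.1 that names the unstructured objectives should be checked at the same time.

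The cost is a few sentences in three or four places, with no new data collection. The PFS denominator becomes about 100 in Phase 2 and at most about 200 once the Phase 3 charts are added, which is what Objective 9 already implies. If PFS in non-front-line patients is wanted, their progression would have to be abstracted, and that would be a real extension of the chart review.
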